4.2.5 Study Drug Exposure and Study Drug Compliance

A summary table of study drug exposure and compliance will be provided. Number of infusions (aducanumab or placebo) received will be summarized as a categorical variable (categories as integers from 1 to 20, and 1-5, 6-10, 11-15, and 15-20) as well as a continuous variable. Number of weeks on study treatment (aducanumab or placebo), calculated as (date of last dose – date of first dose + 29)/7, will be summarized as a categorical variable (every 8 weeks from 0 to ≥ 72 weeks) as well as a continuous variable. Percentage of study treatment taken up to the last dose, calculated as (the actual number of infusions / by the number of infusions a subject is expected to take until the date of last infusion)*100, will be summarized as a continuous variable. This table will be presented by treatment group.

Due to the use of titration regimen in the study and possible dose reduction due to ARIA, another summary table will be provided including the following information: number of total infusions (categories of 1-5, 6-10, 11-15, and 15-20) as well as a continuous variable, number of infusions at each dose level (1 mg/kg, 3 mg/kg, 6 mg/kg and 10 mg/kg, respectively) summarized as a categorical variable as well as a continuous variable, number of subjects with dose increase (placebo to 1 mg/kg, 1 to 3 mg/kg, 3 to 6 mg/kg and 6 to 10 mg/kg, respectively), number of subjects with dose reduction (1 mg/kg to placebo, 3 to 1 mg/kg, 6 to 3 mg/kg and 10 to 6 mg/kg, respectively), maximum dose level received, and cumulative dose (as a continuous variable). This table will be presented by treatment group stratified by ApoE status.

A listing of study drug administration records, including dose level at each infusion, cumulative number of infusions and cumulative dose will be provided. A listing of aducanumab lot numbers will be provided.

A listing of study drug administration records for placebo subjects who received any doses of active treatment will be provided.

4.3 Efficacy Analysis

4.3.1 General Considerations

For efficacy endpoints, the following treatment groups of aducanumab (per randomization) will be evaluated and compared with placebo:

- Aducanumab high-dose (10 mg/kg in ApoE ε4 carriers [including 6 mg/kg for subjects enrolled under protocol versions 1-3 who do not have the opportunity to up-titrate to 10 mg/kg prior to completing Week 78 of the study] and 10 mg/kg in ApoE ε4 non-carriers).
- Aducanumab low-dose (3 mg/kg in ApoE ε4 carriers and 6 mg/kg in ApoE ε4 non-carriers).

All efficacy analyses will be performed on the ITT population. In addition, the primary and secondary endpoints will also be performed on the per-protocol population. The efficacy analysis will be presented by treatment group (per randomization), i.e., aducanumab high-dose, aducanumab low-dose and placebo (analysis display A in Appendix 6.1).

The primary, sensitivity and supplementary analyses for the primary and secondary endpoints are listed in Table 2.

Table 2. Analysis for Primary and Secondary Endpoints

Endpoint	Analysis	Analysis Population	SAP Section
CDR-SB	Primary: Analysis of change from baseline at Week 78 (MMRM)	ITT	4.3.2.1
	Sensitivity: Pattern mixture model (ANCOVA)	ITT	4.3.2.2.1
	Sensitivity: Copy increment from reference method (ANCOVA)	ITT	4.3.2.2.2
	Sensitivity: Imputation by natural disease progression (ANCOVA)	ITT	4.3.2.2.3
	Sensitivity: Tipping point analysis (ANCOVA)	ITT	4.3.2.2.4
	Supplementary: Censoring after intercurrent events (MMRM)*	ITT	4.3.2.3.1
	Supplementary: Per-protocol analysis (MMRM)	Per-protocol	4.3.2.3.2
	Supplementary: Responder analysis (Logistic regression)	ITT	4.3.2.3.3
	Supplementary: Slope analysis (MMRM)	ITT	4.3.2.3.4
	Supplementary: Divergence effect analysis (MMRM)	ITT	4.3.2.3.5
MMSE,	Primary: Analysis of change from baseline at Week 78 (MMRM)	ITT	4.3.3.1,
			4.3.3.2,
			4.3.3.3

CONFIDENTIAL

The information contained herein may not be used, disclosed, or published without the written consent of Biogen MA Inc.

ADAS-Cog 13, ADCS-ADL- MCI	Sensitivity: Pattern mixture model (ANCOVA) Supplementary: Censoring after intercurrent events (MMRM)* Supplementary: Per-protocol analysis (MMRM) Supplementary: Slope analysis (MMRM) Supplementary: Divergence effect analysis (MMRM)	ITT ITT Per-protocol ITT ITT	4.3.3.4 4.3.3.4 4.3.3.4 4.3.3.4 4.3.3.4
---	--	--	---

* Analysis excludes data collected after the following intercurrent events: (1) premature discontinuation of the study treatment and (2) any change to concomitant AD symptomatic medications during the study. All other analyses will include data collected after intercurrent events [ICH E9 (R1) Addendum 2017].

Visit windows for mapping efficacy endpoint

For efficacy data that are summarized or analyzed by visit, data collected on all scheduled visits and all unscheduled visits will be mapped to an appropriate analysis visit using the windowing scheme shown in Table 3. If there are 2 or more assessments available in the same analysis window for a subject, the assessment that is closest to the target visit day will be used for analysis. If there are 2 or more assessments in the same analysis window with the same distance from the target visit day, the later assessment will be used.

Table 3. Visit Windows for Efficacy Endpoints

Analysis visit	Target visit day	Analysis visit window
Baseline	1	Most recent non-missing pre-dose value
Week 26	183	[92, 266]
Week 50	351	[267, 448]
Week 78	547	[449, the end day of the placebo-controlled period *]
* The end day of the placebo-controlled period is the last day before the first infusion in LTE for subjects who enter LTE, and is the last day in study for subjects who do not enter LTE.		

Handling of missing items for scales

If any of the individual items for the primary and secondary endpoints is missing, the total score of the corresponding endpoint will be imputed by prorating the observed scores [van Ginkel 2010].

For ADAS-Cog13, if 3 or fewer of 13 items (<25%) are missing, the total score will be imputed by the following algorithm: Total score = total score from the completed items * [maximum total score (=85) / maximum total score for the completed items]. The imputed number will be rounded up to the nearest integer. If more than 3 items are missing, the total score of ADAS-Cog 13 at that visit will be considered missing.

For ADCS-ADL-MCI, if 4 or fewer of 18 items (<25%) are missing, the total score will be imputed by a similar algorithm as that for ADAS-Cog 13. The imputed number will be

	Statistical Analysis Plan Placebo-Controlled Period	Final V1.0
---	---	-------------------

rounded up to the nearest integer. If more than 4 items are missing, the total score for ADCS-ADL-MCI at that visit will be considered missing.

The same imputation algorithm will be applied to CDR-SB and MMSE, if only 1 box (of 6) of CDR is missing or if only 2 or fewer items (out of 11) are missing for MMSE. If the score from more than 1 box of CDR or more than 2 items of MMSE is not available, the CDR-SB or MMSE at that visit will be considered missing.

The total score of the tertiary endpoint NPI-10 will be imputed using the same prorating principle if only 1 item (out of 10) is missing. For EQ-5D and mPDQ-20, if any item is missing, any total or sum involving that item will be considered missing.

Considerations for multiple comparison adjustments

A sequential (closed) testing procedure will be used to control the overall Type I error rate due to multiple comparisons for the primary endpoint. The order of treatment comparisons is as follows: aducanumab high-dose versus placebo and aducanumab low-dose versus placebo. All comparisons after the initial comparison with $p > 0.05$ will not be considered statistically significant.

Secondary endpoints have been rank prioritized, in the order shown in Section 1.2. In order to control for a Type I error for the secondary endpoints, a sequential closed testing procedure will be used and will include both the order of the secondary endpoints and treatment comparisons. Specifically, for each of the secondary endpoints, a sequential (closed) testing procedure, as for the primary endpoint, will be used to control the overall Type I error rate due to multiple treatment comparisons. If statistical significance is not achieved for 1 or 2 treatment comparisons, all endpoint(s) of a lower rank will not be considered statistically significant for that 1 or 2 treatment comparisons, respectively.

There will be no multiple comparison adjustments for the sensitivity and supplementary analyses for the primary and secondary efficacy endpoints, the tertiary efficacy endpoints, the subgroup analyses or the additional analyses.

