2 STUDY DESIGN

2.1 Study Overview

Study 221AD302 (EMERGE) is a multicenter, randomized, double-blind, placebo-controlled, parallel-group study in subjects with early AD, including mild cognitive impairment (MCI) due to AD and a subset of mild AD, followed by an optional dose-blinded long-term extension (LTE) period of up to 5 years. Approximately 1605 subjects will be enrolled across approximately 150 centers globally. The primary study objective is to evaluate the efficacy of monthly doses of aducanumab on the CDR-SB relative to placebo. Secondary objectives include assessment of the effect of monthly doses of aducanumab on clinical progression as compared to placebo. The safety of monthly doses of aducanumab will also be evaluated.

Table 1: Dosing Scheme for Aducanumab by Treatment Group and ApoE ε4 Carrier Status: Placebo-Controlled Period

Dose (every 4 weeks)		1	2	3	4	5	6	7 to 20
Treatment Group	Treatment Group Stratified by ApoE Status ²	Dose (mg/kg)						
High Dose	High Dose - ApoE ε4 (+)	1	1	3	3	6	6	10 ¹
	High Dose - ApoE ε4 (-)	1	1	3	3	6	6	10
Low Dose	Low Dose - ApoE ε4 (+)	1	1	3	3	3	3	3
	Low Dose - ApoE ε4 (-)	1	1	3	3	3	3	6
Placebo	Placebo - ApoE ε4 (+)	saline						
	Placebo - ApoE ε4 (-)	saline						

¹ 10 mg/kg is the target dose for all ApoE ε4 carriers assigned to the aducanumab high-dose group. Subjects enrolled under protocol versions 1-3 and assigned to the previous high-dose of 6 mg/kg will be titrated to 10 mg/kg upon receipt of at least 2 doses at 6 mg/kg.

² ApoE ε4 status recorded in the Interactive Voice/Web Response System (IXRS).

Subjects will be randomized in a 1:1:1 ratio to 1 of the 3 treatment groups: aducanumab high dose, aducanumab low dose and placebo, with stratification based upon their apolipoprotein E4 (ApoE ε4) carrier status (carrier/non-carrier) and site. During the placebo-controlled period, subjects will receive infusions of aducanumab or placebo approximately every 4 weeks for approximately 18 months (a total of 20 doses). Dose levels may be different in the same treatment group based upon subjects' ApoE ε4 carrier status, and specifically, ApoE ε4

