4 STATISTICAL ANALYSIS METHODS

4.1 General Considerations

This statistical analysis plan (SAP) only covers the analyses for the primary, secondary and tertiary objectives for the placebo-controlled portion of the study. Hereafter, the placebo-controlled portion of the study will be referred to as “the study” in the rest of this SAP (e.g.,

CONFIDENTIAL

The information contained herein may not be used, disclosed, or published without the written consent of Biogen MA Inc.

	Statistical Analysis Plan Placebo-Controlled Period	Final V1.0
---	---	-------------------

completion of the study means completion of the placebo-controlled portion). A separate SAP will be prepared for the analyses of the LTE period and integrated analyses across both portions of the study. The analyses of additional exploratory endpoints will be documented separately.

Summary tables will be presented using descriptive summary statistics. For continuous variables, summary statistics will generally include: number of subjects with data, mean, standard deviation, median, 25% percentile, 75% percentile, minimum and maximum. For categorical variables, this will generally include: number of subjects randomized or dosed, number with data, and the percent of those with data in each category.

There are two types of analysis displays for tables: by treatment group (analysis display A in Appendix 6.1) and by treatment group stratified by ApoE status (analysis display B in Appendix 6.1; here ApoE status refers to the status recorded in IXRS [see Table 1 for correspondence between treatment groups and treatment groups stratified by ApoE status]). The analysis display for each analysis will be defined in each section. All the listings will be presented by treatment group stratified by ApoE status, unless otherwise specified.

Unless otherwise specified, baseline value is defined as the most recent non-missing measurement collected prior to the first dose. Change from baseline will be defined as post-baseline value minus baseline value.

Unless stated otherwise, all statistical tests will be 2-sided with statistical significance level of 0.05.

The statistical software, SAS® will be used for all summaries and analyses.

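### The SAP claims Type I error control for the secondary endpoints, but its rule leaves two tests open at the full 0.05 after a high-dose win, so family-wise error can reach about 9.5%

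*SAP*

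**What the plan says.** All of this is in SAP section 4.3.1, under the considerations for multiple comparison adjustments, except the significance level, which is in section 4.1.

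- **Level:** "all statistical tests will be 2-sided with statistical significance level of 0.05", unless stated otherwise.
- **Dose order for the primary endpoint:** "The order of treatment comparisons is as follows: aducanumab high-dose versus placebo and aducanumab low-dose versus placebo". The stop rule is "All comparisons after the initial comparison with $p > 0.05$ will not be considered statistically significant".
- **Claim for the secondary family:** "In order to control for a Type I error for the secondary endpoints, a sequential closed testing procedure will be used".
- **Endpoint order:** "Secondary endpoints have been rank prioritized, in the order shown in Section 1.2", that is, MMSE, then ADAS-Cog 13, then ADCS-ADL-MCI.
- **Within each secondary endpoint,** the same stop rule holds across the two doses: "for each of the secondary endpoints, a sequential (closed) testing procedure, as for the primary endpoint, will be used to control the overall Type I". The low dose therefore again needs a high-dose win first.
- **Between secondary endpoints:** if one or both comparisons fail, "all endpoint(s) of a lower rank will not be considered statistically significant for that 1 or 2 treatment comparisons, respectively".

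No share of alpha is assigned to either dose.

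**The concern.** The rule between endpoints closes lower ranks only for the comparison that failed. Because the low dose cannot be significant without a high-dose win on the same endpoint, exactly one failure can only mean that the high dose won and the low dose failed. In that case the high dose goes on to the next endpoint at 0.05. A single fixed sequence would have stopped there, so the text cannot be read as one.

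A high-dose win on MMSE thus opens two tests, low-dose MMSE and high-dose ADAS-Cog 13. Each is at the full 0.05 and neither depends on the other. If both nulls are true, their intersection is rejected whenever either test is significant. A closed procedure at 5% must test that intersection at no more than 5%, and this one does not.

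The rule decides which secondary results may be called statistically significant. A claim made under it would not carry the error rate the SAP attaches to it.

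**Working it through.** **Inputs.** The level is two-sided 0.05, so the critical value is 1.96 (section 4.1). Order and stop rules are those of section 4.3.1. Section 2.1 says "Subjects will be randomized in a 1:1:1 ratio to 1 of the 3 treatment groups", so the two dose tests on one endpoint share a placebo group of equal size and have correlation 0.5. The correlation ρ between endpoints is not in the SAP. It is an assumption here, varied from 0 to 1. Low dose on one endpoint and high dose on the next then have correlation 0.5ρ.

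**The rule as coded.** Write H1, H2, H3 and L1, L2, L3 for high and low dose on MMSE, ADAS-Cog 13 and ADCS-ADL-MCI. Hj needs wins on all earlier H. Lj needs a win on Hj and on all earlier L. Every test is at 0.05.

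**Step 1: where the stated 5% is reproduced.** Under the global null a false claim needs a false H1 first, and simulation (1,000,000 runs per setting) gives 0.050. It is also 0.050 when the high dose works on all three endpoints and the low dose on none, and when both doses work on MMSE only.

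**Step 2: the worst case.** The high dose works on MMSE with power near 1, and L1 and H2 are null. A false claim occurs if either L1 or H2 is rejected:

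FWER = 1 − P(|Z_L1| < 1.96 and |Z_H2| < 1.96), with correlation 0.5ρ.

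With independent tests this is 1 − 0.95² = 0.0975. The exact bivariate normal gives:

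| ρ | 0.5ρ | FWER |
|---|---|---|
| 0 | 0 | 0.0975 |
| 0.3 | 0.15 | 0.0969 |
| 0.5 | 0.25 | 0.0959 |
| 0.6 | 0.30 | 0.0951 |
| 0.7 | 0.35 | 0.0943 |
| 1 | 0.5 | 0.0907 |

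Simulation of the whole rule agrees: 0.0972, 0.0958 and 0.0934 at ρ = 0, 0.5 and 0.8. The same maximum recurs one rank down, with L2 and H3 null. At most two true nulls are open in parallel, so the bound is 0.05 + 0.05 = 0.10.

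**Step 3: realistic power for high-dose MMSE.** Now a false claim also needs H1 to be rejected:

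FWER = P(H1 rejected) − P(H1 rejected, neither L1 nor H2 rejected).

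Check at ρ = 0 and 90% power. P(H1 and L1 rejected) is 0.0388 by simulation, and P(H1 and H2 rejected) is 0.9 × 0.05 = 0.045. Because H2 is independent of the other two, the union is 0.0388 + 0.045 − 0.0388 × 0.05 = 0.082. For ρ from 0.7 to 0.3 the result is 6.9% to 7.9% at 90% power and 5.9% to 6.9% at 80% power.

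**Step 4: the alternatives.** One fixed sequence H1, L1, H2, L2, H3, L3 at 0.05 gives at most 0.050 in every configuration, up to simulation error. With the present rule at 0.025 per dose branch, each branch is itself a fixed sequence, so the error is at most 0.025 + 0.025 = 0.05. The Step 2 worst case becomes 1 − 0.975² = 0.0494 for independent tests and 0.0465 at ρ = 1.

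**The case against.** **The maximum is a corner case.** It needs power near 1 for the high dose on one endpoint, no low-dose effect there, and no high-dose effect on the next. An effect on one cognitive scale and exactly none on the next is a narrow pattern, and in several other patterns the error is 5%. This stands as to size: 9.5% is a ceiling, and a reader should not take it as the error rate of the plan. It does not rescue the claim, because section 4.3.1 asserts control without limiting it to the global null.

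**The low dose is not a free branch.** A reader might infer two independent branches, each spending 5% with only the failing dose stopping. The text does not support that. Section 4.3.1 carries the high-then-low order into every secondary endpoint, so a high-dose failure also bars the low dose there and on all lower ranks. Only a low-dose failure leaves the other path open.

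**The missing link to CDR-SB.** A reader might also infer an error across the primary and secondary families together, since section 4.3.1 has no sentence making the secondaries conditional on CDR-SB. The documents do not support that as a finding. The SAP claims control for each family separately and never 5% across both, and the protocol, which is not at hand, may contain the condition. Such a condition would not cure the present problem either, because the two paths would still run in parallel once the secondary tests began.

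**Conclusion.** The stated property is wrong as written. The secondary rule is not a closed test at 5% and does not control the family-wise error strongly. Within the secondary family the error is 5% under the global null and at most 9.1% to 9.75% in the worst case, with roughly 7-8% at 90% power and 6-7% at 80% power for the higher-ranked high-dose test.

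These figures rest on normal test statistics, equal group sizes and an endpoint correlation that the SAP does not give. The conclusion does not depend on that correlation, because even at 1 the worst case is 9.1%. Section 4.3.3.3 bases the primary ADCS-ADL-MCI analysis on data pooled from two studies. That should lower its correlation with the single-study ADAS-Cog 13 test and move that step towards 9.75%.

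The CDR-SB comparison of high dose and then low dose is a valid fixed sequence and is unaffected. The defect concerns only which secondary results may be labelled significant.

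**What to change.** Change the secondary paragraph of section 4.3.1 before unblinding, and leave the primary sequence alone. Any one of these restores 5% control within the secondary family:

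1. One fixed sequence at two-sided 0.05 that stops at the first p > 0.05: MMSE high, MMSE low, ADAS-Cog 13 high, ADAS-Cog 13 low, ADCS-ADL-MCI high, ADCS-ADL-MCI low.
2. The same kind of sequence with the three high-dose tests first, in endpoint order, followed by the three low-dose tests. This lets the high dose continue whatever the low dose shows.
3. The present rule with every secondary test at 0.025, that is, 0.025 for each dose branch.

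If the present rule is kept at 0.05, withdraw the claim of Type I error control across the secondary endpoints.

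The cost is one paragraph of text and some lost reach. Under option 1 a low-dose failure ends high-dose testing on lower ranks. Under option 2 low-dose claims wait for all three high-dose wins, including the pooled ADCS-ADL-MCI test. Under option 3 every secondary test faces a stricter threshold.

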4.3.2 Primary Efficacy Endpoint

4.3.2.1 Primary analysis

The estimand of the primary analysis is the mean difference of the change from baseline CDR-SB scores at Week 78 between treatment groups in the ITT population [ICH E9 (R1) Addendum 2014, 2017]. All observed data will be included in the primary analysis, including data collected after intercurrent events [ICH E9 (R1) Addendum 2017], i.e., treatment discontinuation or a change in concomitant use of AD symptomatic medication.

The change from baseline CDR-SB scores will be summarized by treatment group at each post-baseline visit. A mixed model repeated measures (MMRM) model will be used as the primary analysis to analyze change from baseline CDR-SB using fixed effects of treatment group, time (categorical), treatment group-by-time interaction, baseline CDR-SB, baseline CDR-SB by time interaction, baseline MMSE, AD symptomatic medication use at baseline (yes/no; see Section 4.2.3 for definition of AD symptomatic medication use at baseline),

CONFIDENTIAL

The information contained herein may not be used, disclosed, or published without the written consent of Biogen MA Inc.

region, and laboratory ApoE ϵ 4 status (carrier/non-carrier). An unstructured covariance matrix will be used to model the within-patient variance-covariance errors. If the unstructured covariance structure matrix results in a lack of convergence, the heterogeneous Toeplitz covariance structure followed by the heterogeneous first-order autoregressive covariance structure will be used. The Kenward-Roger approximation will be used to estimate the denominator degrees of freedom. In the primary analysis, missing data are assumed to be missing at random [Rubin 1976].

4.3.2.2 Sensitivity analysis

The following sensitivity analyses will be performed to assess the robustness of the primary analysis to deviation from the missing-at-random assumption. All the sensitivity analyses will be conducted for the ITT population.

4.3.2.2.1 Pattern mixture model

The pattern mixture model (PMM) represents a general and flexible framework to model the predictive distribution of missing data conditional on the observed data [Little 1993, 1994]. It allows formulating assumptions regarding missing data in a transparent and clinically interpretable manner.

In the PMM framework, subjects are grouped into missing patterns so that subjects in the same pattern share similar missingness characteristics. In this analysis, missing patterns will be defined according to the reasons for early withdrawal from study as reported on the electronic case report form (eCRF). The following two patterns will be considered:

- Subjects who withdraw due to reasons that may be related to efficacy, including consent withdrawn, withdrawal by parent/guardian, investigator decision, loss of capacity, change of treatment, and disease progression;
- Subjects who withdraw due to reasons that are unlikely related to efficacy, including adverse event, lost to follow-up, death, pregnancy, relocation, protocol amendment, site terminated by sponsor/investigator, study visit burden, and other.

Subjects who withdraw due to reasons that may be related to efficacy will be penalized and their missing data will be imputed using the copy increment from reference (CIR) method [Carpenter et al. 2013] (see Section 4.3.2.2.2 for description of the CIR method). Subjects who withdraw due to reasons that are unlikely related to efficacy will be handled using the missing-at-random assumption and their missing data will be imputed using the standard multiple imputation method [Rubin 1987]. Subjects with missing data due to reasons other than early withdrawal (such as item missing, out of window, etc.) will be handled using the missing-at-random assumption. For both imputation methods, the following covariates will be included in the imputation model: treatment group, baseline CDR-SB, baseline MMSE, AD symptomatic medication use at baseline (yes/no), region, and laboratory ApoE ϵ 4 status (carrier/non-carrier). Implementation details can be found in Appendix 6.3.2.

The imputed datasets will be analyzed by an analysis of covariance (ANCOVA) model adjusting treatment group, baseline CDR-SB, baseline MMSE, AD symptomatic medication use at baseline (yes/no), region, and laboratory ApoE ϵ 4 status (carrier/non-carrier). The analyzed results from the imputed datasets will be combined based on Rubin's rules [Rubin

1987] assuming that the statistics estimated from each imputed dataset are normally distributed.

If intermediate missing values are encountered (such as data missing at Week 26 but are available at subsequent visits), a Markov chain Monte Carlo (MCMC) method that assumes multivariate normality will be used to impute the intermediate missing values and produce a monotone missing pattern (data with only terminal missing and no intermediate missing) [Li 1988; Schafer 1997].

